**Objectives:**

To assess the efficacy and effects of prone positioning on the respiratory physiology and death rate of patients suffering from covid pneumonia/ acute respiratory distress syndrome.

**Research Questions:**

Does prone positioning increase the oxygen saturation of blood?

Does prone positioning have any effect on the severity of illness- if prone positioning has any benefits in terms of decreased severity of illness or in terms of decreased mortality at 3 months in patients with covid pneumonia?

**Data collecting tool:**

A self-developed, structured questionnaire. The questionnaire includes socio-demographic data of patients along-with parameters of pneumonia severity index.

**Data collection procedure:**

A structured questionnaire is developed and is tested before adopting the final version. Informed consent will be obtained from all the patients prior to inclusion in the study as a part of ethical practice. Data will be collected regarding personal profile/ demography of the patient by interviewing them, detailed history and thorough clinical examination and relevant investigations. Data will be collected from their medical record book/ file as well.

**Study Protocols:**

All the patients who are received in the medical emergency department as a suspected case of covid pneumonia/ acute respiratory distress syndrome (ARDS), will be assessed in the emergency department as per hospital protocols. If admitted for covid pneumonia/ ARDS, the patient will be offered to consent for participation in the study. The patients who themselves cannot consent due to severity of condition, the attendant closest in relation to the patient will be asked about the consent.

Patient will then be randomized through permuted block randomization into either a control or experimental group and shifted to the respective ward.

Complete data will be recorded on the questionnaire and will be considered as the day one of admission of the patient.

Patients in the prone position group will then be guided for prone positioning for eight hours of intermittent prone positioning. Each cycle may be from 30 minutes to 3 hours. Prone positioning was to be done under the supervision of the staff who were trained by the researchers. The prone positioning was to be done by patient him/herself after guidance with assistance if required so that patient is more comfortable.

Researcher will visit each patient twice a day to ensure if the patient was properly getting the prone positioning intervention and to assess if the patient can tolerate it. In case any complication happens due to the manoeuvre, it will be discussed with the lead investigator. The patient will be assessed for fitness to continue being part of the study or to withdraw from the study.

Record of the prone positioning cycles will be maintained by the staff in the patient file.

Seventh day will be the last day of prone positioning. Data will be recorded by the researcher on seventh day of admission at least ten minutes after the patient has been put to supine position.

Data will also be collected at 14th day of admission of the patient, if the patient is still in the ward.

Patient survival at 90th day will be confirmed by calling the patient/ attendant and requesting for death certificate in case the patient died after discharge from the facility.

**Analyses:** Data will be analysed on SPSS version 25. Statistical tests will be applied to see effect of prone positioning on the severity of covid pneumonia and acute respiratory distress syndrome and to find out its effects on mortality and respiratory physiology – PaO2, respiratory rate and oxygen requirement as determined by the type of oxygen delivery mask, with a confidence interval of 95%. P value of <0.05 will be considered statistically significant. Data will be presented in tables, bar charts, and pie diagrams. Tests of significance will be applied to see effects of prone positioning on respiratory physiology and Kaplan Meier curve will be obtained to compare the survival of the two groups.

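### Entry spans a wide severity range, but the planned 90-day survival comparison makes no stated use of baseline severity, which costs precision

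*Combined protocol and SAP*

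**What the plan says.** All places are in the combined protocol and SAP.

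- **Who enters (Study Protocols).** "If admitted for covid pneumonia/ ARDS, the patient will be offered to consent for participation in the study". The text sets no severity limit, and the sickest are expressly provided for: "The patients who themselves cannot consent due to severity of condition, the attendant closest in relation to the patient will be asked about the consent".
- **Allocation (Study Protocols).** "Patient will then be randomized through permuted block randomization into either a control or experimental group and shifted to the respective ward". No stratification factor, block size or allocation ratio is given.
- **Severity data (Data collecting tool).** "The questionnaire includes socio-demographic data of patients along-with parameters of pneumonia severity index".
- **Timing (Study Protocols).** After the allocation sentence comes: "Complete data will be recorded on the questionnaire and will be considered as the day one of admission of the patient". In the order written, the baseline record follows allocation and the move to the ward.
- **Analysis (Analyses).** Unspecified statistical tests are promised for severity, mortality and respiratory physiology. For survival, a "Kaplan Meier curve will be obtained to compare the survival of the two groups". The threshold is stated as "P value of <0.05 will be considered statistically significant". No covariate, stratum, named survival test or adjusted model appears.

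Mortality is part of the stated objective, and mortality at 3 months is in the research questions.

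**The concern.** Permuted blocks balance the number of patients per arm, not their prognosis. Where entry runs from patients who can position themselves to patients who cannot consent, severity is likely to be a strong predictor of death by day 90. A survival comparison that ignores it has two weaknesses. First, if one arm happens to receive more of the severe patients, the observed mortality difference moves by an amount unrelated to treatment, and the plan gives the reader no adjusted result to set beside it. Second, the between-patient variation due to severity stays in the error term, so the trial has less chance of detecting a real effect than its own data allow. The severity parameters are to be collected anyway; the plan simply does not say that the survival analysis will use them.

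**Working it through.** The plan states no sample size, power, event rate or effect size, so there is no figure of its own to reproduce. What follows is illustration.

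**Inputs from the document:** two arms, permuted blocks, 90-day survival, 0.05 threshold (sidedness not stated; two-sided assumed).

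**Assumed inputs:** 1:1 allocation; 30 to 200 patients per arm; severe share s of 30% to 50%; 90-day mortality 10% in less severe patients (mL) and 40%, 50% or 60% in severe patients (mS).

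**1. How often the arms differ in severity.** Treat the severe counts in the two arms as independent binomials with s = 0.30. The exact probability that the shares differ by 10 points or more is 0.481 at 30 per arm, 0.326 at 50, 0.142 at 100 and about 0.03 at 200. A simulation with actual blocks of 4 and s = 0.40 gave 36% at N = 100 in total and 17% at N = 200.

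**2. What an imbalance does.** Shift = imbalance × (mS − mL). For 10 points:

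- 0.10 × (0.40 − 0.10) = 3 points
- 0.10 × (0.50 − 0.10) = 4 points
- 0.10 × (0.60 − 0.10) = 5 points

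For scale, take s = 0.30 and mS = 0.50. Overall mortality is m = 0.30 × 0.50 + 0.70 × 0.10 = 0.22. The standard error of the mortality difference is √(2 × 0.22 × 0.78 / n), which is 10.7 points at n = 30 per arm, 8.3 at 50 and 5.9 at 100. A 4-point shift is therefore about 0.4, 0.5 and 0.7 of one standard error.

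**3. Share of the variance due to severity.** This is s(1 − s)(mS − mL)² / [m(1 − m)], which does not depend on n. With s = 0.30:

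- mS = 0.40: 0.0189 / 0.1539 = 12%
- mS = 0.50: 0.0336 / 0.1716 = 20%
- mS = 0.60: 0.0525 / 0.1875 = 28%

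**4. Type I error and power.** Simulation: blocks of 4, s = 0.40, 6,000 trials per setting, death by day 90 as a binary outcome. An unadjusted two-proportion test is compared with a severity-stratified Mantel-Haenszel test, which stands in for the stratified log-rank test. Entries are rejection rates in %.

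| N | mL / mS | True risk ratio | One list, unadjusted | One list, stratified test | Two lists, unadjusted | Two lists, stratified test |
|---|---|---|---|---|---|---|
| 100 | 10/40 | 1.0 | 5.3 | 5.3 | 3.8 | 5.2 |
| 100 | 10/60 | 1.0 | 5.2 | 5.0 | 2.1 | 4.9 |
| 200 | 10/40 | 1.0 | 5.1 | 5.2 | 3.4 | 4.6 |
| 200 | 10/60 | 1.0 | 5.6 | 5.2 | 1.9 | 4.7 |
| 100 | 10/40 | 0.6 | 22.5 | 23.0 | 20.3 | 22.4 |
| 100 | 10/60 | 0.6 | 28.7 | 34.2 | 27.2 | 35.4 |
| 200 | 10/40 | 0.6 | 37.1 | 39.5 | 36.3 | 40.2 |
| 200 | 10/60 | 0.6 | 52.1 | 61.2 | 50.7 | 60.9 |

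The Monte Carlo standard error of one entry is at most √(0.25 / 6,000) = 0.65 points, so differences of about a point between lists are noise. A separate run (s = 0.30, mortality 10%/50%, risk ratio 0.5, 100 per arm) gave 56% power unadjusted and 62% with the stratified test.

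**Reading the table.**

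- With one list, the stratified test gains 0.5, 2.4, 5.5 and 9.1 points of power in the four settings.
- Two lists with an unadjusted test gain nothing and make the test conservative (type I error 1.9% to 3.8%).
- Once the test is stratified, the second list adds essentially nothing to power.
- Among null trials with an imbalance of 10 points or more, the unadjusted test rejects in 7% to 9% at N = 100 and 8% to 15% at N = 200. The stratified test rejects in 4.7% to 5.7%.

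**The case against.** **Chance imbalance is random error.** Randomisation makes the unadjusted test valid, and its ordinary confidence interval already allows for such variation. This stands. A reader might infer that the comparison is biased or that false positives are inflated; overall type I error of 5.1% to 5.6% does not support that. The higher rates after an imbalance describe a subset of possible trials, offset by lower rates in the rest.

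**Silence is not exclusion.** The Analyses section promises unspecified tests for mortality as well as the Kaplan-Meier curves, and the severity index parameters are collected. An adjusted analysis is neither planned nor ruled out. This also stands: the gap is that the use of severity is not prespecified, not that the plan forbids it.

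**The severity range may be narrower than it looks.** Patients are expected to turn themselves, with help if needed, and oxygen need is graded by the type of mask. Both suggest mainly awake patients. The attendant-consent provision does admit sicker ones, but their share is unknown. A narrower range would shrink every figure above.

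**Missing randomisation strata are a design preference.** The calculations agree: the analysis does the work, not the lists.

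**A convenient stratum may not exist yet.** It is tempting to say that the emergency assessment already sorts ARDS from pneumonia without ARDS. The Study Protocols section says only that patients are assessed under hospital protocols, so that cannot be assumed.

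**Conclusion.** The point holds as a modest matter of efficiency and prespecification. The plan enrols across a wide severity range, collects severity parameters, and describes a survival comparison that does not use them. The cost is precision, together with the absence of an adjusted result should the arms differ by chance. It is not a validity failure, and the lack of stratified blocks is not in itself an error.

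The size depends on figures that the text reviewed does not give. Under the assumptions shown, the power lost ranges from almost nothing (severe mortality 40%, N = 100) to about 9 points (severe mortality 60%, N = 200). Large imbalances become rare as the trial grows: about 3% at 200 per arm with 30% severe. The direction of the conclusion is firm; the magnitude is illustrative. I would rate it a worthwhile improvement rather than a required correction.

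**What to change.** **Analyses section.** Prespecify that 90-day survival will be compared with a log-rank test stratified by a defined baseline severity group, shown beside the Kaplan-Meier curves. A Cox model adjusted for the baseline pneumonia severity index is an acceptable alternative. Define the groups, or the form of the covariate, before outcomes are examined, and state which result is the main one.

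**Study Protocols section.** State that the severity measure is recorded before the allocation is drawn. As written, the day-one record comes after patients know their arm and have moved ward, which leaves the stratifying variable open to influence by allocation.

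**Optional, only if recruitment has not started.** Draw allocation from a separate permuted-block list for each severity group. This is worth doing only with the stratified analysis; alone, it makes the unadjusted test conservative.

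**If recruitment is under way.** Leave the lists as they are and apply the stratified test, using severity information that the medical record shows was documented before allocation.

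**Cost.** One additional variable at entry and one line in the analysis. Severity must be captured before allocation in a busy emergency setting, and if separate lists are used, one block per list may be left incomplete. Few groups should be used, so that no stratum becomes too thin.

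### A complication of proning can take a patient out of the study, in the prone arm only, with no stated follow-up or as-randomised analysis to protect the comparison

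*Combined protocol and SAP*

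**What the plan says.** Under Study Protocols, allocation comes first: "Patient will then be randomized through permuted block randomization into either a control or experimental group and shifted to the respective ward". The intervention is then assigned to one group: "Patients in the prone position group will then be guided for prone positioning for eight hours of intermittent prone positioning".

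A rule for complications follows: "In case any complication happens due to the manoeuvre, it will be discussed with the lead investigator". The next sentence gives the consequence: "The patient will be assessed for fitness to continue being part of the study or to withdraw from the study". The two outcomes named are staying in the study and leaving it. Ending the positioning while remaining under follow-up is not described, and controls have no corresponding rule.

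Outcome data are planned for day 7, for day 14 if the patient is still in the ward, and for day 90, when survival "will be confirmed by calling the patient/ attendant and requesting for death certificate in case the patient died after discharge from the facility". All three are worded generally, and none mentions withdrawn patients.

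Under Analyses, a "Kaplan Meier curve will be obtained to compare the survival of the two groups". That section names no analysis population, no censoring rule for withdrawals and no method for missing data.

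**The concern.** The decision is made after randomisation, and it is triggered by an event that only one arm can have. If it removes patients from the data, the prone arm becomes a selected subset while the control arm stays intact, and randomisation no longer protects the comparison.

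The plan does not say that these patients are excluded. It leaves three treatments open: delete them, censor them at withdrawal in the Kaplan-Meier analysis, or follow and count them all. These can give different answers, and the choice could be made after the data are seen.

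Two things are at stake. The first is the mortality comparison, since mortality at 3 months is one of the stated research questions. The second is harm reporting: the patients who could drop out of the results are those who had a complication of the intervention.

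**Working it through.** **Inputs.** The sections available give no sample size, mortality rate or withdrawal rate, so there is no figure of the plan's own to reproduce. From the documents: two randomised groups, significance at P < 0.05 (sidedness not stated; two-sided is used here), proning up to day 7, and survival to day 90. Assumed: no true effect, 90-day mortality p = 0.30 in both arms, n = 100 per arm. Varied: w, the share of the prone arm withdrawn, and r, the mortality of withdrawn patients relative to the whole arm.

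**Case 1: withdrawn patients deleted.** The mortality seen in the remaining prone patients is

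p1 = (p − w·r·p) / (1 − w).

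Example with w = 0.10 and r = 2: p1 = (0.30 − 0.10 × 2 × 0.30) / 0.90 = 0.24 / 0.90 = 0.2667, so the apparent risk ratio is 0.2667 / 0.30 = 0.889.

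The type I error uses an unpooled normal approximation with 100 controls and 90 prone patients:

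- SE = √(0.30 × 0.70 / 100 + 0.2667 × 0.7333 / 90) = 0.0654
- shift = (0.30 − 0.2667) / 0.0654 = 0.51
- two-sided rejection probability = P(Z > 1.96 − 0.51) + P(Z < −1.96 − 0.51) = 0.0735 + 0.0068 = 0.080

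The same steps for other values (n = 100 per arm, p = 0.30):

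| r | w | p1 | Risk ratio | Type I error |
|---|---|---|---|---|
| 2 | 2% | 0.2939 | 0.980 | 0.051 |
| 2 | 5% | 0.2842 | 0.947 | 0.057 |
| 2 | 10% | 0.2667 | 0.889 | 0.080 |
| 2 | 20% | 0.2250 | 0.750 | 0.209 |
| 1.5 | 10% | 0.2833 | 0.944 | 0.057 |
| 1.5 | 20% | 0.2625 | 0.875 | 0.086 |
| 1 | any | 0.3000 | 1.000 | 0.050 |
| 0.5 | 10% | 0.3167 | 1.056 | 0.057 |
| 0.5 | 20% | 0.3375 | 1.125 | 0.084 |

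Sensitivity, with r = 2 and w = 10% or 20%:

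- 200 per arm: type I error 0.111 or 0.368.
- 15% mortality, 100 per arm: 0.063 or 0.116.
- A pooled-variance test instead of the unpooled one (30% mortality, 100 per arm, w = 10%): 0.079, so the choice of test hardly matters.

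**Case 2: withdrawn patients censored.** This was simulated with exponential death times and 30% mortality at day 90 in both arms. Withdrawn patients were censored uniformly over days 1 to 7, in the prone arm only. The analysis was Kaplan-Meier with a log-rank test, n = 100 per arm, 20,000 runs.

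| r | w | Prone 90-day mortality (control 30%) | Type I error |
|---|---|---|---|
| 2 | 2% | 29.4% | 0.051 |
| 2 | 5% | 28.6% | 0.055 |
| 2 | 10% | 26.9% | 0.078 |
| 2 | 20% | 23.0% | 0.180 |
| 1.5 | 10% | 28.4% | 0.057 |
| 1.5 | 20% | 26.3% | 0.082 |
| 0.5 | 10% | 31.6% | 0.056 |
| 0.5 | 20% | 33.7% | 0.083 |

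With r = 1 the estimate stays at 30.0% and the error at 0.050 to 0.052. Censoring therefore gives almost the same bias as deletion, because censoring linked to prognosis is informative.

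**After the fix.** If every randomised patient is followed to day 90 and counted in the assigned arm, bias from this source is zero and the error stays at 0.05.

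**The case against.** The strongest reply is that the bias needs a step the plan never describes. Exclusion is not stated. The day-90 call is worded for patients in general, and the two groups compared can naturally be read as the two randomised groups. The sentence on fitness may use the word study loosely to mean the intervention, and withdrawal is one possible result of a case-by-case review, not an automatic one.

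The sizes are also assumed. The route is narrow: a complication, attributed to the manoeuvre, discussed, and then judged to make the patient unfit to continue. Nothing in the documents supports 10% to 20% leaving this way, or doubled mortality among them. With 5% withdrawn at 1.5 times the mortality, the risk ratio is 0.974 and the type I error 0.052. Only mortality is quantified, and the log-rank test in the simulation is not named in the plan.

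Much of this stands: size and direction are unknown, and at low withdrawal the effect is trivial. But the documents do not exclude the larger values either. The gentler reading does not remove the gap. A patient who has left the study is not clearly someone the study still calls, and the call does not supply day-7 or day-14 data. Withdrawals for other reasons could occur in either arm, but the only written rule acts on one. The opening part of the document was not available for review; the follow-up and analysis sections, where such a provision would be expected, were available and do not contain it.

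**Conclusion.** The concern holds. Taken literally, the plan has a post-randomisation rule that can remove patients from the prone arm alone, and no stated follow-up or as-randomised analysis counteracts it.

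Bias is possible, not certain. It arises only if withdrawn patients are deleted or censored and their prognosis differs from the rest of the prone arm. It favours proning if they are sicker and goes against it if they are healthier. Under the assumptions above it is negligible at about 2% withdrawn and becomes material at about 10% or more when prognosis differs strongly. The largest figures, type I errors of 0.209 and 0.180 at 100 per arm, need both 20% withdrawn and doubled mortality. Confidence is high that the text leaves this open; the actual size cannot be determined from the documents. It should be fixed because prevention is cheap.

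**What to change.** Leave the clinical decision about the manoeuvre as it is. Add one or two sentences to Study Protocols and one to Analyses that state:

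- Stopping the manoeuvre does not end participation in the study.
- Day-7 data, day-14 data (if the patient is still in the ward) and the day-90 call are still obtained unless consent is withdrawn.
- All patients are analysed in the arm to which they were randomised, including in the Kaplan-Meier comparison.
- Complications, stopped proning and withdrawals are tabulated by arm.

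No visits are added, since the day-90 call is already planned. The one small downside is that the estimated effect then includes patients who stopped proning and may be smaller.

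### Day-14 data come only from patients still in the ward, and the severity and physiology tests have no rule for death, discharge or withdrawal, so these comparisons risk selection bias of unknown size and direction

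*Combined protocol and SAP*

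**What the plan says.** The Study Protocols section sets two in-hospital assessments after baseline.

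- **Day 7:** "Data will be recorded by the researcher on seventh day of admission", after the patient has been returned to supine. Nothing is said about patients who died or went home earlier. That only inpatients are measured is a fair inference, not a stated rule.
- **Day 14:** the condition is explicit. Data are taken on the 14th "day of admission of the patient, if the patient is still in the ward".

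The only contact described after discharge is the day-90 survival check.

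The same section describes how patients are allocated and how they may leave the study. They are "randomized through permuted block randomization into either a control or experimental group and shifted to the respective ward". On complications it says "In case any complication happens due to the manoeuvre, it will be discussed with the lead investigator", and then "The patient will be assessed for fitness to continue being part of the study or to withdraw from the study". It does not say what happens to the data of a patient who is withdrawn.

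The Analyses section says "Tests of significance will be applied to see effects of prone positioning on respiratory physiology". It lists PaO2, respiratory rate and "oxygen requirement as determined by the type of oxygen delivery mask", and also plans tests of severity. It gives no time point, analysis set or rule for patients who died, were discharged or were withdrawn. Survival is compared separately by Kaplan-Meier curve.

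**The concern.** Randomisation protects a comparison of everyone randomised. Being in the ward on day 7 or day 14 is decided afterwards, and the documents give three reasons why it could differ by arm.

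1. The trial asks "if prone positioning has any benefits in terms of decreased severity of illness or in terms of decreased mortality at 3 months". If proning works, it changes who has died, who has gone home and who remains.
2. Each arm is housed in its own ward, and discharge practice may differ between wards.
3. Withdrawal is raised directly after complications of the manoeuvre, so that exit is open mainly to the prone arm. This route is weaker than the other two: a withdrawn patient may still be in the ward, and loss of the data is inferred.

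Severity and respiratory physiology are among the trial's stated questions. A difference in them, or its absence, could partly reflect who is left to measure rather than an effect of proning.

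**Working it through.** The documents give no death, discharge or withdrawal rate, effect size or sample size, so there is no figure of the plan's own to reproduce. What follows is an illustration, and **every input is assumed**.

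**Model.** Severity S (higher is worse) is N(0,1) in control and N(−d,1) in the prone arm, so d is the true benefit in SD. Exit depends on L = ρS + √(1−ρ²)·e, with e standard normal. A patient has died if L is above an upper cut-off and has been discharged if L is below a lower one. With M the mean of standardised L between the cut-offs, M = [φ(lower) − φ(upper)] / (proportion remaining). Mean severity in the ward is ρM in control and −d + ρM in the prone arm, with the prone cut-offs expressed relative to that arm's own mean of L. The ward-only difference, control minus prone, is therefore d + ρ(M_control − M_prone). Positive means apparent benefit.

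**Control arm, 20% died and 50% discharged.** The cut-offs are 0 and 0.8416, so M = (0.39894 − 0.27996)/0.30 = 0.3966.

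**No true effect, prone arm discharges 60%, deaths 20%.** The lower cut-off is 0.2533, so M = (0.38634 − 0.27996)/0.20 = 0.5319. The difference is ρ(0.3966 − 0.5319), which is −0.068 at ρ = 0.5 and −0.095 at ρ = 0.7: apparent harm.

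**True benefit 0.30, same cut-offs in both arms.** The benefit itself shifts prone exits; at ρ = 0.5 they become about 16% died and 56% discharged.
- ρ = 0.5: prone M = 0.3880 + 0.15 = 0.5380; difference 0.30 + 0.5(0.3966 − 0.5380) = 0.229.
- ρ = 0.7: prone M = 0.3846 + 0.21 = 0.5946; difference 0.30 + 0.7(0.3966 − 0.5946) = 0.161.

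**Other patterns**, from the same formula:

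| True benefit | Control died/discharged | Prone died/discharged | Ward-only difference, ρ = 0.5 / 0.7 |
|---|---|---|---|
| 0.30 | 20/50% | 20/40% | 0.365 / 0.391 (exaggerated) |
| 0.10 | 20/50% | 15/60% | −0.008 / −0.051 (reversed) |
| 0 | 20/50% | 15/55% | −0.073 / −0.102 (equal total exit, different mix) |
| 0 | 20/50% | 20/50%, plus the sickest 5% of the arm among those alive and in hospital withdrawn, data lost | 0.036 / 0.050 |
| 0 | 10/10% | 10/15% | −0.038 / −0.054 |
| 0 | 10/10% | 10/5% | 0.043 / 0.060 |
| 0.30 | 20/50% | 20/50% | 0.300 / 0.300 (no bias) |

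The two 10/10% rows are meant to resemble an earlier time point such as day 7.

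**Choice of repair, by simulation.** Assumed: 100 per arm, three mask steps, death as the worst level, two-sided 0.05, tie-corrected Wilcoxon test. Discharged patients are placed either by last mask type or in a best category of their own.
- No true effect, discharges 50% against 60%: the version with discharge as the best level favours proning in 17 to 18% of trials. The last-mask version rejects in about 2 to 3% on each side. The ward-only t-test rejects in 5 to 8% in total, mostly against proning.
- True benefit 0.30, same cut-offs with 70% exit in control: power is about 37 to 40% for last-mask, 18 to 27% for discharge-as-best and 13 to 17% for the ward-only t-test.

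These results for the last-mask version assume that oxygen need does not change after discharge.

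**The case against.** The strongest reply has four parts.

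- **Day 14 may be only descriptive.** The Analyses section names no day, so a reader might infer a committed day-14 test that the text does not contain. This stands, and it is why the point is conditional on a test being made. Nothing in the plan rules such a test out.
- **Exits may be alike.** If each kind of exit has the same rate and the same relation to severity in both arms, a constant effect is estimated without bias. This also stands. Equal total exit is not enough, as the 15/55% row shows. If the effect varies with severity, the ward-only result applies to ward patients and not to all randomised.
- **Every magnitude is assumed.** True. A reader might infer that the trial's results will be biased, or biased in favour of proning. The documents support neither; the sign changes with the exit pattern.
- **A composite may be worse than the problem.** This is correct for the obvious composite with discharge as the best level. It is more sensitive than the ward-only test to a difference in discharge practice, one of the routes named above. The fix is chosen accordingly.

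A reader might also extend the point to 90-day survival. That does not follow: survival is sought after discharge and does not depend on being in the ward.

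**Conclusion.** The concern holds as a risk, and the plan should be changed. What rests on the text is the explicit ward condition at day 14 and the absence of any rule for exits in the Analyses section. The inpatient-only reading of day 7 and a test at day 14 are inferences. The size rests wholly on assumption: with 20% died, 50% discharged and a correlation of 0.5 to 0.7, a true 0.30 SD benefit can appear as 0.16 to 0.23, and no effect can appear as harm of 0.07 to 0.10 SD. Other patterns exaggerate or reverse the effect. Day 7 is less exposed than day 14 only if few patients have left by then, which the documents do not say.

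**What to change.** **Minimum:** in the Analyses section, state which day each test uses and how deaths, discharges, withdrawals and transfers are handled.

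**Recommended:**
- Make day 7 the main time point.
- Analyse oxygen requirement in all randomised patients, by assigned arm, as an ordered outcome: mask steps in an order written down in advance, a level for ventilation if it occurs, and death as the worst level. Use a Wilcoxon rank test or a proportional-odds model.
- For patients discharged before that day, use the last mask type in the file as the main analysis. Use discharged alive as the best level only as a sensitivity analysis, because the arms are in separate wards.
- Classify withdrawn or transferred patients by their status that day where known. Otherwise count them as missing by arm, with a best/worst-case analysis.
- Keep the planned PaO2, respiratory rate and severity tests, labelled as conditional on being in the ward. Beside them, report the numbers dead, discharged, withdrawn and in the ward by arm.

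**Cost:** no new visit or call is needed, since the patient file is already a data source and the day-90 call is already planned. Status and last mask type must be extracted for every randomised patient. The ordered outcome combines death with oxygen need, so it answers a different question from PaO2 alone and does not give a mean difference. The main version rests on oxygen need being unchanged after discharge, which should be stated with the result.
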